### **6.1.2 Clinical Procedures/Assessments**

#### **6.1.2.1 Adverse Event (AE) Monitoring**

The investigator or qualified designee will assess each subject to evaluate for potential new or worsening AEs as specified in the Trial Flow Chart and more frequently if clinically indicated. Adverse experiences will be graded and recorded throughout the study and during the follow-up period according to NCI CTCAE Version 4.03 (see Appendix 1). Toxicities will be characterized in terms regarding seriousness, causality, toxicity grading, and action taken with regard to trial treatment.

For subjects receiving treatment with pembrolizumab all AEs of unknown etiology associated with pembrolizumab exposure should be evaluated to determine if it is possibly an event of clinical interest (ECI) of a potentially immunologic etiology.

Please refer to section 6.2 for detailed information regarding the assessment and recording of AEs.

#### **6.1.2.2 Full Physical Exam**

The investigator or qualified designee will perform a complete physical exam during the screening period. Clinically significant abnormal findings should be recorded as medical history. A full physical exam should be performed during screening and repeated as per the frequency defined in the Trial Flow Chart. After the first dose of trial treatment new clinically significant abnormal findings should be recorded as AEs.

#### **6.1.2.3 Directed Physical Exam**

For cycle days that do not require a full physical exam per the Trial Flow Chart, the investigator or qualified designee will perform a directed physical exam as clinically indicated prior to trial treatment administration. New clinically significant abnormal findings should be recorded as AEs.

#### **6.1.2.4 Vital Signs**

The investigator or qualified designee will take vital signs at screening, prior to the administration of each dose of trial treatment and at treatment discontinuation as specified in the Trial Flow Chart (Section 5.0). Vital signs should include temperature, pulse, respiratory rate, weight and blood pressure. Height will be measured at screening only.

#### **6.1.2.5 Eastern Cooperative Oncology Group (ECOG) Performance Scale**

The investigator or qualified designee will assess ECOG status at screening, prior to the administration of each dose of trial treatment and discontinuation of trial treatment as specified in the Trial Flow Chart.

#### **6.1.2.6 Electrocardiogram (ECG)**

A standard 12-lead ECG will be performed using local standard procedures at Screening. Clinically significant abnormal findings should be recorded as medical history.

#### **6.1.2.7 Eastern Cooperative Oncology Group (ECOG) Performance Scale**

The investigator or qualified designee will assess ECOG status at screening, prior to the administration of each dose of trial treatment and discontinuation of trial treatment as specified in the Trial Flow Chart.

#### **6.1.2.7.1 Myeloma Disease Measurements**

##### Primary Myeloma Panel

The Primary Myeloma Panel that the Investigator followed for subject's disease status should be specified on trial eCRF. Along with other Myeloma Markers, the clinical site should consistently record and follow the Primary Myeloma Panel throughout the trial.

##### Monoclonal Protein Considerations

Laboratory tests for measurement of Serum M-protein level are quantitated using densitometry on SPEP except in cases where the SPEP is felt to be unreliable such as in patients with IgA monoclonal proteins migrating in the beta region. If SPEP is not available or felt to be unreliable (e.g., in some cases of IgA myeloma) for routine M -protein quantitation during therapy, then quantitative immunoglobulin levels on nephelometry or turbidometry can be accepted. However, this must be explicitly reported, and only nephelometry can be used for that patient to assess response and SPEP and nephelometric values cannot be used interchangeably.

Urine M-protein measurement is estimated using 24-h UPEP only. Random or 24 h urine tests measuring kappa and lambda light chain levels are not reliable and are not recommended.

See Appendix 5 for Myeloma Response Criteria.

#### **6.1.2.7.2 Criteria for Assessment of Disease**

Multiple Myeloma: International uniform response criteria for multiple myeloma[57].

The International Working Group criteria will be applied by the site as the primary measure for assessment of disease response and as a basis for all protocol guidelines related to disease status (e.g., discontinuation of trial treatment).

#### **6.1.2.8 Disease Assessment of Immunotherapeutic Agent**

Immunotherapeutic agents such as pembrolizumab (MK-3475) may produce antitumor effects by potentiating endogenous cancer-specific immune responses, which may be functionally anergic. The response patterns seen with such an approach may extend beyond the typical time course of responses seen with cytotoxic agents, and can manifest a clinical response after an initial increase in tumor burden or even the appearance of new lesions. Standard response assessment criteria may not provide a complete response assessment of immunotherapeutic agents such as pembrolizumab (MK-3475). Therefore in the setting where a subject's assessment shows PD, study drug should not be discontinued unless

progression is confirmed at least 3 weeks later, provided that the subject's clinical condition is stable.

#### **6.1.2.9 Timing of Disease Assessments**

Uniform disease response assessment will be performed every 21-day treatment cycle.

#### **6.1.2.10 Initial Disease Assessment**

Initial disease assessments must be performed within 28 days prior to the first dose of trial treatment (See 5.0 – Trial Flow Charts).

Bone marrow aspirates/biopsies performed as part of standard of care prior to signing informed consent may be used for screening if performed within 28 days of Day 1.

Myeloma laboratory disease assessments should be performed within 28 days prior to the first dose of trial treatment (See 5.0 – Trial Flow Charts).

#### **6.1.2.11 Disease Assessment during Trial**

Disease assessments should be performed per the frequency defined in Section 5.0 – Trial Flow Charts. There is a  $\pm 3$  day window for assessments performed after Day 1. Disease assessments should not be delayed for delays in cycle starts.

Disease assessments should continue to be performed until documented disease progression, the start of new anti-cancer treatment, withdrawal of consent, death, or the end of the study, whichever occurs first. Disease assessments should be performed to confirm stringent CR or as clinically indicated.. Subjects who have unconfirmed disease progression may continue on treatment until progression is confirmed at the next scheduled assessment.

#### **6.1.2.12 Confirmation Assessments**

A subject with progression of disease may continue trial treatment until confirmation of progression of disease is documented per the respective response evaluation criteria at least 21 days later. Subjects may only receive treatment while waiting for confirmation of PD if the following criteria are met:

- Absence of signs and symptoms (including worsening of laboratory values) indicating disease progression;
- No decline in ECOG performance status
- Absence of rapid progression of disease.
- Absence of progressive tumor at critical anatomical sites (e.g. cord compression) requiring urgent alternative medical intervention.

After the first disease response assessment, it is at the discretion of the investigator to keep a clinically stable subject on trial treatment or to stop trial treatment until a repeat assessment is performed at least 21 days later. When feasible, subjects should not be discontinued until repeat disease response assessment is performed at least 21 days later.

(See Section 5.0 for Trial Flow Chart and Procedures Manual for further details).

### 6.1.3 Laboratory Procedures/Assessments

Details regarding specific laboratory procedures/assessments to be performed in this trial are provided below. The total amount of blood/tissue to be drawn/collected over the course of the trial (from pre-trial to post-trial visits), including approximate blood/tissue volumes drawn/collected by visit and by sample type per subject can be found in the Procedures Manual.

Table 10 Laboratory Tests

Hematology	Chemistry	Urinalysis	Other
Hematocrit	Albumin	Blood	Serum $\beta$ -human chorionic gonadotropin ( $\beta$ -hCG)
Hemoglobin	Alkaline phosphatase	Glucose	PT (INR)
Platelet count	Alanine aminotransferase (ALT)	Protein	aPTT
WBC (total and differential)	Aspartate aminotransferase (AST)	Specific gravity	Total Thriodothyronine (T3) †
Red Blood Cell Count	Bicarbonate	Microscopic exam, if abnormal results are noted	Free tyroxine (T4)
Absolute Neutrophil Count	Calcium	Urine pregnancy test*	Thyroid stimulating hormone (TSH)
	Chloride		
	Creatinine		
	GFR		
	Uric Acid		
	Calcium		
	Glucose		
	LDH		

Phosphorus			
Potassium			
Sodium			
Magnesium			
Total Bilirubin			
	Direct Bilirubin, if total bilirubin is elevated above the upper limit of normal		
	Total protein		
	Blood Urea Nitrogen		

\* Perform on women of childbearing potential only. If urine pregnancy results cannot be confirmed as negative, a serum pregnancy test will be required.

† Free T3 may be performed in place of Total T3 per local standards

Laboratory tests for Screening or entry into the Second Course Phase should be performed within 10 days prior to the first dose of treatment. After Cycle 1, pre-dose laboratory procedures can be conducted up to 72 hours prior to dosing. Results must be reviewed by the investigator or qualified designee and found to be acceptable prior to each dose of trial treatment.

#### **6.1.3.1 Pharmacokinetic/Pharmacodynamic Evaluations**

There will be no pharmacokinetic or pharmacodynamics sampling for this protocol.

#### **6.1.4 Other Procedures**

##### **6.1.4.1 Withdrawal/Discontinuation**

When a subject discontinues/withdraws from participation in the trial, all applicable activities scheduled for the final trial visit should be performed at the time of discontinuation. Any adverse events which are present at the time of discontinuation/withdrawal should be followed in accordance with the safety requirements outlined in the protocol. Visit Requirements

Visit requirements are outlined in Section 5.0 - Trial Flow Chart.

## **6.1.4.2 Screening**

### **6.1.4.2.1 Screening Period**

Approximately 28 days prior to enrollment, potential subjects will be evaluated to determine that they fulfill the entry requirements as set forth in Section 4.1. Visit requirements are outlined in Section 5.0 – Trial Flow Chart.

Written consent for the main study must be obtained prior to performing any protocol specific procedure. Results of a test performed prior to the subject signing consent as part of routine clinical management are acceptable in lieu of a screening test if performed within the specified time frame. Screening procedures are to be completed within 28 days prior to the first dose of trial treatment except for the following:

- Female subject of childbearing potential should have a negative serum or urine pregnancy test within 72 hours prior to receiving retreatment with study medication.

Subjects may be rescreened after initially failing to meet the inclusion/exclusion criteria. Results from assessments performed during the initial screening period are acceptable in lieu of a repeat screening test if performed within the specified time frame and the inclusion/exclusion criteria is met.

## **6.1.4.3 Treatment Period**

### **6.1.4.4 Post-Treatment Visits**

#### **6.1.4.4.1 Safety Follow-Up Visit**

The mandatory Safety Follow-Up Visit should be conducted approximately 30 days after the last dose of trial treatment or before the initiation of a new anti-cancer treatment, whichever comes first. All AEs that occur prior to the Safety Follow-Up Visit should be recorded. Subjects with an AE of Grade > 1 will be followed until the resolution of the AE to Grade 0-1 or until the beginning of a new anti-neoplastic therapy, whichever occurs first. SAEs that occur within 90 days of the end of treatment or before initiation of a new anti-cancer treatment should also be followed and recorded.

#### **6.1.4.5 Follow-up Visits**

Subjects who discontinue trial treatment for a reason other than disease progression will move into the Follow-Up Phase and should be assessed every 12 weeks ( $84 \pm 7$  days) to monitor disease status. Every effort should be made to collect information regarding disease status until the start of new anti-neoplastic therapy, disease progression, death, end of the study. Information regarding post-study anti-neoplastic treatment will be collected if new treatment is initiated.

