## 1.0 TRIAL DESIGN

### 1.1 Trial Design

This is an open-label, Phase II, single center trial of pembrolizumab (MK-3475), lenalidomide and dexamethasone in subjects with high risk Multiple Myeloma (hrMM) post high-dose chemotherapy with autologous stem cell transplantation (ASCT).

Pembrolizumab (MK-3475), [name], HUMC

Patients with high-risk MM defined as those with one of the following abnormalities who have undergone induction therapy followed by single or tandem melphalan -based ASCT will be considered eligible.

1. International Staging System (ISS) stage 3 (See Appendix 3 for ISS Staging) and/or
2. Deletion 13q by cytogenetics and/or
3. 1q amplification, 1p deletion, p53 deletions (17p deletions), t(4;14), t(14;16), t(14;20), hypodiploidy by FISH and/or
4. High-risk gene expression profile (GEP) scores

Post engraftment, between days +60 and day +180 post ASCT patients will undergo restaging evaluation to include a screening BM aspirate and biopsy. Patients will then be initiated on pembrolizumab, lenalidomide and dexamethasone for 2 cycles followed by pembrolizumab and lenalidomide alone for 2 cycles for a total period of 4 months.

Adverse events will be monitored at every visit and graded in severity according to the guidelines outlined in the NCI Common Terminology Criteria for Adverse Events (CTCAE) version 4.03. (See Appendix 1).

Treatment with pembrolizumab, lenalidomide and dexamethasone for the first 2 cycles then pembrolizumab and lenalidomide will continue for cycle 3 and 4 for a total of four cycles or until unacceptable adverse event(s), documented confirmed disease progression, intercurrent illness that prevents further administration of treatment, investigator's decision to withdraw the subject, subject withdraws consent, pregnancy of the subject, noncompliance with trial treatment or procedure requirements, or administrative reasons. After the completion of cycle 4, each subject will be followed for 30 days for adverse event monitoring (serious adverse events will be collected for 90 days after the end of treatment). Subjects who discontinue treatment for reasons other than disease progression will have post-treatment follow-up for disease status until disease progression, initiating a non-study cancer treatment, withdrawing consent, or becoming lost to follow-up. All subjects will be followed by telephone contact for overall survival until death, withdrawal of consent or the end of the trial, whichever comes first.

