The primary objectives of this trial are to establish the progression free survival (PFS) of ASCT followed by consolidative therapy with pembrolizumab plus lenalidomide and dexamethasone and to evaluate the safety of pembrolizumab plus lenalidomide and dexamethasone following ASCT. The immunological analysis of cells and cytokines pre and post-therapy will be determined from patient bone marrow aspirate and peripheral blood samples as exploratory objectives. The overall composition of the gut microbiome will also be determined in patient stool samples.

Patients will be followed by response, EFS/PFS/OS and safety endpoints on an every 3 week basis. Bone marrow aspirate specimens will be obtained at screening and at completing of the

[figure not shown]
Pembrolizumab (MK-3475), [name], HUMC

study and peripheral blood specimens will be obtained on a monthly basis to evaluate in correlative studies.

This trial will be conducted in conformance with Good Clinical Practices. Specific procedures to be performed during the trial, as well as their prescribed times and associated visit windows, are outlined in the Trial Flow Chart – Section 5.0.

An interim efficacy analysis will be performed after 15 patients are accrued. The study will stop and treatment will be rejected if there are more than 8 patients ( $\geq 9$  patients) who progress at 12 months. If 8 or more of the first 15 patients have not progressed at 12 months, a further 26 patients will be recruited into the second stage. If the overall PFS is 70% or above at 12 months, pembrolizumab, lenalidomide and dexamethasone will be considered to have shown worthwhile efficacy.

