#### 4.1.2 Subject Inclusion Criteria

In order to be eligible for participation in this trial, the subject must:

1. Be willing and able to provide written informed consent/assent for the trial.
2. Be  $\geq 18$  years of age on day of signing informed consent.
3. Has a confirmed diagnosis of MM based on standard criteria. (See Appendix 2 for MM Diagnostic Criteria.)

4. Is between 60 and 180 days from peripheral blood autologous stem cell transplant.

5. At diagnosis, had MM with measurable disease, defined as:

- A monoclonal immunoglobulin spike on serum electrophoresis of at least 0.5 g/dL and/or
- Urine monoclonal levels of at least 200 mg/24 hours
- For subjects without measurable serum and urine M-protein levels, an abnormal free light chain (FLC) ratio (normal value 0.26 – 1.65) with involved FLC  $\geq 10$  mg/dL
- Radiographic evidence of disease for those without measurable M-spike or free light chains.

6. Has high-risk MM, which must be present at the time of diagnosis, and defined by:

- a. International Staging System (ISS) stage 3 (See Appendix 3 for ISS Staging), and/or
- b. Deletion 13q by cytogenetics, and/or
- c. 1q amplification, 1p deletion, p53 deletions (17p deletions), t(4;14), t(14;16), t(14;20), hypodiploidy, and/or
- d. High-risk gene expression profile (GEP) scores

7. Be able to provide a newly obtained bone marrow aspirate/biopsy material for biomarker analysis and disease assessment.

8. Have a performance status of  $\leq 2$  on the ECOG Performance Scale (See Appendix 4).

9. Demonstrate adequate organ function as defined in Table 1, all screening labs should be performed within 28 days of treatment initiation.

Table 1 Adequate Organ Function Laboratory Values

System	Laboratory Value
Hematological	
Absolute neutrophil count (ANC)	$\geq 1,000$ /mcL
Platelets	$\geq 75,000$ / mcL
Hemoglobin	$\geq 8$ g/dL or $\geq 5.6$ mmol/L without transfusion or EPO dependency (within 7 days of assessment)
Renal	
Serum creatinine OR Measured or calculated a creatinine clearance (GFR can also be used in place of creatinine or CrCl)	$\leq 1.5$ X upper limit of normal (ULN) OR $\geq 60$ mL/min for subject with creatinine levels $> 1.5$ X institutional ULN
Hepatic	

Serum total bilirubin	
	$\leq 1.5 \times \text{ULN}$ OR
	Direct bilirubin $\leq \text{ULN}$ for subjects with total bilirubin levels $> 1.5 \text{ ULN}$
AST (SGOT) and ALT (SGPT)	

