Quantitative serum immunoglobulins 	X	X		X		X		X		X	
Serum protein electrophoresis and serum immunofixation 	X	X		X		X		X		X	
Serum free light chain analysis 	X	X		X		X		X		X	
24 hour urine protein electrophoresis and urine immunofixation 	X	X		X		X		X		X	
M-protein quantitation (urine and/or serum) 	X	X		X		X		X		X	
Beta-2 microglobulin 	X	X		X		X		X		X	
Bone marrow aspiration and biopsy 	X							X			
Trial Period:	Treatment Cycles						End of Treatment	Post-treatment			
		Cycle = 21 Days									
Treatment Cycle/Title:	Screening (Visit 1)	Cycle 1	Cycle 2	Cycle 3 and 4	At the completion of cycle 4	Post-Treatment Safety Follow-up	Follow-up Visits 	Survival Follow-up 			

Cycle Day					1	15				30 days post completion of cycle 4	Every 12 weeks post completion	
	1	8	15		1	15			Cycle 4	of	post Discon	Every 12 weeks
Bone marrow morphology, IHC, cytogenetics by standard karyotyping, FISH panel, and minimal residual disease (MRD) analysis 		X 17, 19			X 17		X 17		X			
Correlative Studies – bone marrow and peripheral blood collection, stool samples 	X 6	X 6			X		X		X			

1. In general, assessments/procedures are to be performed on Day 1 and prior to the first dose of treatment for each cycle unless otherwise specified. Treatment cycles are 21 days. Unless otherwise noted, procedures should be on Day 1 of each Cycle.
2. Procedures outlined for visit, 30-day Safety-Follow-up and Survival Follow-up should be performed for subjects who complete the study or progress.
3. Subjects who discontinue trial treatment for a reason other than disease progression will move into the Follow-Up Phase and should be assessed every 12 weeks (84 ± 7 days) to monitor disease status. Every effort should be made to collect information regarding disease status
4. In general, the window for each visit is ± 3 days unless otherwise noted.
5. Record all medications taken from 28 days prior to cycle 1 day 1 to the 30 day post completion of cycle 4 visit.
6. For correlative studies, collection will be at screening or cycle 1 day 1, then every day 1 of each cycle, and at completion of cycle 4 and to confirm response.

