7. After documented disease progression or the start of new antineoplastic therapy, each subject will be followed by telephone for overall survival until death, withdrawal consent or the end of the trial, whichever occurs first.
8. AEs and laboratory safety measurements will be graded per NCI CTCAE version 4.03. All AEs, whether gradable by CTCAE or not, will also be evaluated for seriousness. AEs will be evaluated every two weeks, on Days 1 and 15 of each 21-day cycle.
9. Record all AEs occurring within 30 days after the last dose of study drug. Report all SAEs (related and unrelated to trial treatment) and ECIs occurring up until 90 days after the last dose of trial treatment or the start of new anti-cancer treatment, whichever comes first. Afterwards, report only SAEs and ECIs that are related to trial treatment.
10. Directed PE performed to collect any new/clinically significant abnormalities (i.e. ECI/AE).
11. Vital signs to include temperature, pulse, respiratory rate, weight and blood pressure. Height will be measured at screening only.
12. Skeletal survey should include a chest (PA or AP; lateral), skull (lateral), upper extremities (shoulder to elbow), lower extremities (hip to knee; AP), pelvis (AP), cervical/thoracic/lumbar spine (AP and lateral). For suspected progression to bone disease bidimensional measurement of the target lytic lesions must be performed. MRI/CT/PET (MRI for subjects with bone disease and CT/PET for plasmacytomas) is required when clinically indicated for subjects with bony disease and should just include the bony lesions. Subjects with measurable plasmacytomas at baseline should have imaging performed every 12 weeks.
13. Disease response assessment is based upon the multiple myeloma response criteria (See Appendix 5 ). Myeloma lab assessments should be performed every 3 weeks, that is, on Day 1 of every 21-day treatment cycle. Disease assessments should occur at Day 1 of each 21-day treatment cycle (+/- 7 days) throughout the course of the trial.

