##### **7.1.6.1 Efficacy Endpoints**

Key efficacy endpoints for the trial include the following as assessed by IMWG:

- PFS: defined as the time from Day 0 of ASCT to progressive disease (PD) or death, whichever occurs earlier, per IMWG criteria by investigator assessment. Subjects without documented PD/death will be censored at the last disease assessment date.
- Complete response, stringent complete response, and very good partial response rate (CR + sCR + VGPR) rate using IMWG criteria. Response rates will be determined with the following baselines 1) Prior to ASCT 2) Cycle 1 day 1 of study drug or screening visit, whichever is higher.
- ORR: Defined as the proportion of subjects who have achieved sCR, CR, VGPR or PR according to the IMWG criteria by investigator assessment. Subjects with missing outcome on objective response will be considered non-responders. Response rates will be determined with the following baselines 1) Prior to ASCT 2) Cycle 1 day 1 of study drug or screening visit, whichever is higher.
- DOR: defined as the time interval between the date of first response (sCR, CR, VGPR, PR) and the date of first documented disease progression.
- TTP: defined as the time from 1) Day 0 ASCT and 2) Date of enrollment to progressive disease (PD) per IMWG criteria by investigator assessment. Subjects without documented PD or death will be censored at the last disease assessment date, and subjects who died without documented PD will be censored at the time of death.

- OS: defined as the time from Day 0 ASCT to death from any cause.

In addition, overall survival (OS) and change from baseline in bone marrow/aspirate PD-L1 expression, T-cell subsets, and cytokine analysis will be evaluated.

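### No disease assessment is tied to 12 months from transplant, and the plan gives conflicting post-treatment schedules, so progressions shortly before day 365 can count as successes

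*Combined protocol and SAP*

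**What the plan says.** **Endpoint and decision.** Section 7.1.6.1 has PFS "defined as the time from Day 0 of ASCT to progressive disease (PD) or death". Without documented progression or death, the patient is censored at the last disease assessment. Sections 7.1.3 and 7.1.12 apply the two-stage rule to patients progression-free at 12 months: 9 or more of 15 to continue, then (7.1.3) 27 or more of 43 to reject.

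**Start of treatment.** Section 4.1.2 admits a patient who "Is between 60 and 180 days from peripheral blood autologous stem cell transplant". Section 1.1 plans treatment "for a total of four cycles", and flow chart footnote 1 says "Treatment cycles are 21 days", so treatment lasts 84 days.

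**Assessments after treatment, 12-weekly.** Under Section 6.1.4.5, patients who stop treatment without progression "will move into the Follow-Up Phase and should be assessed every 12 weeks", with a window of 84 ± 7 days. The anchor is in the flow chart, whose follow-up column counts the 12 weeks from completion.

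**Assessments after treatment, 3-weekly.** Section 1.1 states: "Patients will be followed by response, EFS/PFS/OS and safety endpoints on an every 3 week basis". Flow chart footnote 13 states: "Disease assessments should occur at Day 1 of each 21-day treatment cycle", and goes on to apply this across the whole trial. That footnote is attached to the follow-up cell of the response-criteria row.

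**A second progression date.** Section 3.2.3.1 dates progression at the start of the next line of therapy or at death, not at IMWG progression.

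**The concern.** The endpoint clock starts at ASCT, but the visit clock starts at the end of treatment. Because treatment can start anywhere in a window of about four months, the visits around day 365 fall on different days for different patients, and none is placed at 12 months.

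The effect on the trial's own count goes one way. A progression that occurs before day 365 but is first found at the next visit is dated after day 365, and the patient counts as progression-free at 12 months. This can affect both the stage 1 decision and the final one. Kaplan-Meier estimation does not remove it, because progression enters the curve on the date it is found. Dating progression by the next line of therapy could delay it further.

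The conflicting schedules matter in themselves: staff who follow different sections would obtain different primary counts from the same patients.

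**Working it through.** **1. Reproduce the plan's design.** With X1 ~ Bin(15, p) and X2 ~ Bin(28, p), P(pass | p) = sum over x = 9 to 15 of P(X1 = x) × P(X2 ≥ 27 − x).
- p = 0.50: pass 0.0499, early termination 0.696, expected size 23.5.
- p = 0.70: pass 0.804.

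These match Section 7.1.3. (Section 1.1 gives other stage counts; I use those of 7.1.3.)

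**2. Visit days.** For a treatment start s days after ASCT, treatment ends at s + 84 and follow-up visits fall every 84 days after that. The gap from the last scheduled assessment to day 365 is g = (365 − s) mod 84.

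| Start (day) | Last visit by day 365 | Next visit | Gap (days) |
|---|---|---|---|
| 60 | 312 | 396 | 53 |
| 120 | 288 | 372 | 77 |
| 180 | 348 | 432 | 17 |

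**3. Average gap.** The documents give no distribution of start days. Assuming starts uniform on days 60 to 180, the mean gap is 39.5 days (0 to 83 in whole days). Only 24% of start days put a scheduled visit within 14 days of day 365. The mean is 38.8 days if starts run to day 208 (28-day screening added), 39.6 days with the ± 7-day window simulated, and 33 to 47 days for narrower start ranges inside the window.

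**4. Apparent 12-month rate.** Assume constant hazard from ASCT, λ = −ln(p)/365, and detection only at scheduled visits. The apparent rate is the mean of exp(−λ(365 − g)).
- True 50%: λ = 0.00190 per day. At the mean gap, 0.5 × exp(0.00190 × 39.5) = 0.539; averaging over all start days also gives 0.539.
- True 70%: apparent 0.728.

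**5. Effect on the decision rule at a true 50%.**

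| Case | Apparent rate | P(pass) |
|---|---|---|
| Assessment at day 365 | 0.500 | 0.050 |
| 12-weekly, scheduled visits only | 0.539 | 0.126 |
| 12-weekly, half of the shift remains | 0.520 | 0.081 |
| 3-weekly throughout (mean gap 9.8 days) | 0.509 | 0.064 |

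In the second case, early termination falls from 0.696 to 0.58. At a true 70%, the pass probability rises from 0.804 to 0.884.

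**6. Sensitivity to the hazard.** If all hazard falls after treatment start (patients already progressing at screening are excluded), a true 50% reads as 56.2% and the pass probability is about 0.19.

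**The case against.** **Events can be found between visits.** Section 6.1.2.11 allows assessments when clinically indicated, Section 6.1 allows unscheduled procedures, and deaths are dated when they happen. This stands: under constant hazard from ASCT, 0.13 is an upper-end figure, and the half-shift value of 0.08 allows for it.

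**The 3-weekly text may govern.** If so, the mean gap is about 10 days and the effect is small. The documents do not settle this, so both readings have to be shown. It is a reason to reconcile the text, not to leave it.

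**The benchmark may carry the same delay.** Section 3.2.1.2 reports a 50% 12-month PFS in high-risk patients in an earlier trial. A reader might infer from the table that the trial's false-positive rate against this benchmark rises from 5% to 13%. The documents do not support that. The inference needs the 50% to be free of visit delay, and the earlier trial's schedule is not given. If its assessments were evenly placed before day 365 (assumed intervals), the same model gives about 0.09 for 4-weekly visits, 0.07 for 8-weekly and 0.05 for 12-weekly. With matching schedules the excess disappears.

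**Spaced assessments counted from treatment are ordinary.** True, but here the decision is a count at one fixed time from a different origin, so the misalignment enters the primary result directly.

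**Conclusion.** The point holds as a defect of alignment and consistency. PFS is timed from ASCT, both decisions are read at 12 months, no assessment is tied to that time, and the sections disagree on whether assessment after treatment is 12-weekly or 3-weekly.

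On the 12-weekly reading the trial's own count is biased upward. The mean gap is about 40 days, assuming uniform starts on days 60 to 180. Under constant hazard from ASCT, the shift at a true 50% is up to about 4 percentage points. The corresponding pass probability is about 0.13 with detection only at scheduled visits, about 0.08 with half of the shift, and about 0.06 on the 3-weekly reading, against 0.05.

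These figures describe the count within this trial. They are not an established type I error against the historical rate, for which the net error is unknown. The change should be made, because it removes an avoidable bias from the primary count at small cost.

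**What to change.** 1. Reconcile Section 1.1, the flow chart with footnotes 3 and 13, and Section 6.1.4.5 to one post-treatment assessment schedule.
2. Shift the follow-up schedule so that one existing assessment falls at 12 months from ASCT within a stated window, for example ± 14 days. Base the 9/15 and 27/43 counts on status at that assessment.
3. State how a patient with no assessment in the window is counted.
4. Use one progression date: the first of the two consecutive IMWG assessments that confirm progression. Remove the next-line-of-therapy definition from Section 3.2.3.1.

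**Cost.** The text changes are limited to these sections and 7.1.3, 7.1.6.1 and 7.1.12. No procedure is added, but one visit interval per patient may depart from 84 ± 7 days. At worst the nearest scheduled visit is 42 days from day 365 (start at day 155: visits at 323 and 407), so it must move 42 − 14 = 28 days to enter the window.

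The 12-month rate may also come out slightly less favourable, including against a historical rate that was itself read at spaced visits. If the 70% target reflects 12-weekly reading, an exact day-365 assessment would correspond to about 66.8%, and the pass probability would be about 0.68 instead of 0.80. The sponsor should therefore state, as far as it can be found, how the historical rate was assessed.
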